Screening will be administered by data clerks and counsellors trained on the PHQ-2 and PHQ-9,³² which have been locally validated in Malawi.³³ The PHQ-2 assesses frequency of depressed mood and anhedonia, and it has been implemented throughout Africa.³⁵⁻³⁷ Administration of the PHQ-2 by data clerks as a first step has the potential to save time, given the number of attendees at IC3. Those who score 0 will not advance to the remaining PHQ-9 questions. Patients who screen positive with the PHQ-2 (score > 0; range: 0-6) will immediately receive remaining PHQ-9 questions from a counsellor. A PHQ-9 score ≥ 10 (range: 0-27) represents a possible depressive disorder.^{32,38} Those with PHQ-9 < 10 (PHQ-9 score of 5-9 indicates mild depressive symptoms) will receive a brief, manualized psychoeducation session, and counsellors will inform patients that screening will continue at IC3 on an ongoing basis. Those with PHQ ≥ 10 (moderate/severe depression) will proceed to receive a brief diagnostic interview adapted from the Composite International Diagnostic Interview (CIDI) 3.0, a structured diagnostic interview designed for the assessment of mental disorders by lay interviewers.^{1,2} This has been widely used throughout sub-Saharan Africa as part of the World Mental Health Survey.^{1,4} The depression module of the CIDI 3.0 corresponds to DSM-IV diagnostic criteria, on which 5 or more depressive symptoms for ≥ 2 weeks and functional impairment indicates a diagnosis of depression.¹ Counselors will be trained to administer the brief diagnostic interview and—analogue to the PHQ-9—those for whom a diagnosis of depression is not concluded will receive a brief, manualized psychoeducation session.

Figure 3. Care Pathways for Control and Intervention Arms

Treatment: Usual Care

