Supervision will be conducted one-on-one with counselors and clinical officers – and provided by a lead clinician. Supervision will be weekly for first month, then every other week for 3 months, and then monthly thereafter. Supervisors will be available 24/7 for suicide or emergency consultations. Regarding fidelity, supervisors will review charts of clients receiving ADT, and at each monthly supervision meeting assess adherence to the treatment protocol. For PM+, we will develop a checklist for the supervisors to use to rate fidelity to each component of the protocol for PM+.

Primary Outcomes

Measures will include surveys, laboratory assays, pharmacy data, and data abstracted from medical charts. Survey measures that have not been translated into Chichewa in the course of prior research will be translated using standard translation, back-translation methods, and will be administered at each assessment, unless otherwise noted.

Depression prevalence and severity. Depression symptoms will be measured with the PHQ-9,³⁸ which has been translated previously and locally-validated.³³ We have elected to use PHQ-9 because it has been implemented throughout sub-Saharan Africa, including Malawi, where the scale has shown high sensitivity responding to treatment, as well as concurrent and predictive validity.^{7,57-61} It contains nine four-point ordinal response items on topics such as hopelessness, psychosomatic response (e.g. sleeplessness, loss of appetite) and anhedonia. We will derive two

outcome measures from this: (i) depression prevalence among patients attending the clinic; and (ii) depression severity among those with depression. The numerator for the former is all those who screen positive as on the PHQ-9 ($\text{PHQ-9} \geq 10$), the denominator is all active adult patients at IC3. The latter measure will be the PHQ-9 score.

Functional impairment. Functional impairment including aspects of daily functioning, correspond to DSM diagnostic criteria.⁶² We will evaluate this using the 12-item WHO Disability Assessment Schedule 2.0 (WHODAS).⁶³ The WHODAS has been validated in a diverse range of sub-Saharan African contexts, including Malawi,^{64,65} and covers topics like completing household chores, concentrating, and maintaining relationships.

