Integrating a Stepped Care Model of Screening and Treatment for
Depression into Malawi's National HIV Care Delivery Platform

(ID: R01MH117760)

Statistical Analysis Plan

Analysis of Primary Outcomes

This analysis plan concerns the primary outcomes of the IC3D intervention trial. However, analyses of the secondary outcomes will follow the same procedure with appropriate changes for the nature of the outcome.

We will have primary outcomes at two levels. At the aggregate cluster-time level we have

1. Prevalence of depression

As we do not capture data on those who do not have depression that would enable us to link individual screening outcomes between time periods, we will only be able to collect total number screened and total number with depression for each cluster at each time period (i.e. "step").

At the individual level, among those who are diagnosed with depression we will collect:

2. Depression severity among those with depression (PHQ-9)
3. WHODAS score among those with depression
4. EQ-5D-3L utility score and those with depression

If the intervention is successful then it should have the effect of reducing the overall prevalence of depression among those with chronic conditions, and also reduce the severity of depression and improve the quality of life among those with depression in this group of patients.

The data derived from the trial will be analysed using a generalised linear mixed model framework standard for stepped-wedge cluster designs.[1] Several trial guidelines, including the influential CONSORT statement,[2,3] recommend the specification of a single primary outcome to avoid a multiple comparisons problem. However, given the complex, multifaceted nature of this health service delivery intervention, no single outcome can adequately describe the effect of the intervention and be used to judge its effects. As a result, we have specified several primary outcomes and will "correct" or modify our analyses to account for the multiple outcomes problem.

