There are two main types of approach to dealing with multiple outcomes: multivariate methods and univariate methods. The former method works by jointly modelling all the outcomes at once. However, the joint model of the four outcomes is highly complex, potentially with non-linear sub-models, two-stage models, and shared random effects to allow for correlation (see Appendix), which makes inference difficult or even infeasible without development (and evaluation) of custom software (e.g. a Monte Carlo Maximum Likelihood sampler), which is out of the scope of this project. Instead, we will model the outcomes separately and use a method to correct the family-wise error rate (a univariate methodology).

Statistical model

Aggregate cluster-time outcome

For cluster $j = 1, \dots, J$ at time period $t = 1, \dots, T$ we will screen n_{jt} patients of whom $y_{jt}^{(1)}$ will be diagnosed with depression such that

$$y_{jt}^{(1)} \sim \text{Binomial}(n_{jt}, p_{jt})$$

where we will specify a logistic regression model:

$$\log\left(\frac{p_{jt}}{1-p_{jt}}\right) = z'_{jt}\gamma_1 + \delta_1 D_{jt} + \alpha_{j,1} + \phi_{jt,1}$$

where z_{jt} is a vector of cluster-level covariates, and $\alpha_j \sim N(0, \sigma_\alpha^2)$ and $\phi_{jt} \sim N(0, \sigma_\phi^2)$ are cluster and cluster-time random effects, respectively.

Individual-level outcomes

For patient $i = 1, \dots, N$ who has depression the outcome is $y_{ijt}^{(k)}$ for outcomes $k = 2, 3, 4$. For each outcome we specify the linear model:

$$y_{ijt}^{(k)} = x'_{ijt}\beta_k + z'_{jt}\gamma_k + \delta_k D_{(i)jt} + \theta_{i,k} + \alpha_{j,k} + \phi_{jt,k} + e_{ijt,k}$$

where x_{ijt} is a vector of patient-level covariates $\theta_i \sim N(0, \sigma_\theta^2)$ is an individual-level random effect and e_{ijt} is an independent, identically distributed error term.

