The implementation outcomes are divided into three categories:

1. Screening:
 - a. Proportion of patients screened with the PHQ-2, out of those attending IC3 clinics.
 - b. Proportion screening positive with PHQ-2, out of those who were administered the PHQ-2.
 - c. Proportion screened on the PHQ-9, out of those who screened positive on the PHQ-2.
 - d. Proportion screening positive on PHQ-9, out of those who were administered the PHQ-2.
2. Diagnosis:
 - a. Proportion of patients who are administered the BDIS, out of those who screened positive on the PHQ-9.
 - b. Proportion of patients who receive a diagnosis using BDIS, out of those administered the BDIS.
3. Treatment:
 - a. Proportion of patients attending treatment sessions (PM+, ADT, both), out of those who have been enrolled in the IC3D clinical trial and elected to receive treatment (PM+, ADT, both)
4. Protocol Fidelity:
 - a. Proportion of reviewed mastercards appropriately completed by clinical officers
 - b. Proportion of patient registration forms appropriately completed by counsellors
 - c. Proportion of PM+ components appropriately covered within each PM+ therapy session

Each step is a potential point of failure that could limit the acceptability or effectiveness of the intervention. Analysis of the implementation outcomes constitutes a descriptive analysis intended to support interpretation of trial results.

We will report the overall trial mean proportions of each implementation outcome along with 95% confidence intervals. Note that the screening and diagnosis outcomes are available for both treatment and control conditions, while the treatment outcomes are only available in treatment units. We will also examine the temporal changes in the implementation outcomes by reporting within each three-month block mean proportions and associated uncertainty intervals.

Secondary analyses

In addition to the usual issues of adherence, such as patients refusing treatment or not attending scheduled treatment, we have identified that patients diagnosed in one month or trial “block” may not be treated until the subsequent month or trial block. At an individual level, non-adherence would

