Outcomes 2-4 described above are only recorded for those who screen positive for depression at their scheduled visit as these instruments are not used for other patients in the trial. For each time period (quarterly), any patient eligible for screening (i.e. in the "denominator population") will have a value for recorded for Outcome 1 equal to one if they screen positive and meet the pre-defined criteria for entry into the depression care programme, or zero otherwise. The model is thus a "two-stage" type model with only those with defined depression contributing data from Outcomes 2-4 to the likelihood. Letting Y represent all the data, the log-Likelihood is therefore:

$$\begin{aligned} \log L(\theta|Y, \Phi) &= \log f(Y; \theta, \Phi) \\ &= \sum_{i=1}^n \left(1 - y_{ijk}^{(1)}\right) \log\left(1 - g_1\left(\eta_{ijt}^{(1)}\right)\right) \\ &\quad + y_{ijk}^{(1)} \left(\log\left(g_1\left(\eta_{ijt}^{(1)}\right)\right) + \log f_2\left(y_{ijt}^{(2)}; \theta, \Phi\right) + \log f_3\left(y_{ijt}^{(3)}; \theta, \Phi\right)\right) \\ &\quad + \log f_2\left(y_{ijt}^{(3)}; \theta, \Phi\right) + \log f_\phi(\Phi; \omega) \end{aligned}$$

where ω are the parameters of the joint distribution of random effects. The likelihood function for the parameters alone is determined by integrating out the random effects Φ and then maximising the resulting likelihood. Given the complexity of our model including non-linear effects, two-stage models, and multiple shared random effect terms, there exists no "out of the box" software that could reliably be used. Instead an alternative approach, such

as Monte Carlo Maximum Likelihood would be required. Given the technical complexity required, and any simulation-based testing that would be required to ensure any custom-built sampler was functioning correctly, we instead opted for a univariate methodology.

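### Primary outcome 1 scores patients who drop out between the PHQ-2 and diagnosis as not depressed, so a change in completion when a clinic switches would bias the prevalence effect in either direction

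*SAP*

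**What the plan says.** Outcome 1 is analysed by clinic and three-month step. SAP, Analysis of Primary Outcomes, says that "we will only be able to collect total number screened and total number with depression for each cluster at each time period", because patients without depression cannot be linked across periods. Under Aggregate cluster-time outcome, n_jt patients are screened and y_jt of them "will be diagnosed with depression such that" y_jt is binomial with n_jt trials. Neither place says which part of the cascade counts as being screened.

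The SAP Appendix gives the fullest coding. Every patient eligible for screening gets a value "equal to one if they screen positive and meet the pre-defined criteria for entry into the depression care programme, or zero otherwise". That text belongs to the joint model, which the SAP did not adopt.

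The protocol, under Primary Outcomes, defines prevalence differently. A case is a PHQ-9 score of at least 10, with no interview, and "the denominator is all active adult patients at IC3".

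The route to diagnosis is in the protocol under Study Participants and Eligibility Criteria:
- Data clerks give the PHQ-2 ("Administration of the PHQ-2 by data clerks as a first step has the potential to save time").
- Patients scoring above 0 "will immediately receive remaining PHQ-9 questions from a counsellor".
- Those with PHQ-9 of 10 or more then have a diagnostic interview, also given by counsellors.

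The SAP addendum measures completion of the PHQ-9 among PHQ-2 positives (item 1c) and of the interview among PHQ-9 positives (item 2a). It remarks: "Each step is a potential point of failure that could limit the acceptability or effectiveness of the intervention". It says these data exist in both conditions, but plans only descriptive reporting, as trial means and by three-month block. SAP, Missing Data, deals with missed appointments, no-shows and data entry error, with multiple imputation as a secondary analysis when more than 10% is missing.

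**The concern.** A patient who is PHQ-2 positive but never gets the PHQ-9, or who scores 10 or more but never gets the interview, attended and was screened but has unknown depression status. Followed as written, the plan turns that unknown into a non-case. This does little harm to the comparison if completion is the same before and after a clinic switches. If completion differs, the difference enters delta_1, the log odds ratio for prevalence. The planned re-randomisation test gives no protection, because a change in recorded cases caused by the switch looks to it like a treatment effect.

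The planned block summaries do not separate the two explanations. In protocol Figure 1 no clinic is under intervention in period 1 and all are by period 6, so clinic state and calendar time move together across blocks.

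**Working it through.** **Inputs from the documents.** 14 clinics and 30 enrollees per clinic per step (protocol, Study Design and Sample Size); 10% prevalence, ICC 0.05, CAC 0.80, two-sided 0.05 (Sample Size); an alternative prevalence of 19% (Introduction); principal analysis on months 1 to 18, which is 6 periods (Analysis of Intervention Effects).

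**Plan's own figure.** 14 x 30 = 420 enrollees per step, as stated. At 10% prevalence, 30 enrollees imply 30 / 0.10 = 300 screened per clinic-step.

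**Assumed.** All completion rates, because the documents give none.

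**Formula.** Take a true case as a patient who would be diagnosed if the cascade were finished. Then observed prevalence = true prevalence x completion among true cases, and OR = [b/(1-b)] / [a/(1-a)], with a before and b after the switch. True prevalence is held constant, so the correct OR is 1.00.

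| Completion before → after | Observed before → after | OR |
|---|---|---|
| One step, 95% → 90% | 9.5% → 9.0% | 0.94 |
| One step, 95% → 85% | 9.5% → 8.5% | 0.885 |
| One step, 90% → 70% | 9.0% → 7.0% | 0.76 |
| Both steps, 95% → 90% each | 9.0% → 8.1% | 0.89 |
| Both steps, 95% → 85% each | 9.0% → 7.2% | 0.785 |
| One step, 80% → 90% | 8.0% → 9.0% | 1.14 |
| Unchanged at 100% | 10% → 10% | 1.00 |

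Worked line, both steps: 0.10 x 0.95 x 0.95 = 0.09025 and 0.10 x 0.85 x 0.85 = 0.07225; OR = (0.07225/0.92775) / (0.09025/0.90975) = 0.785. At 19% prevalence, one step falling from 95% to 85% gives 18.05% → 16.15%, OR 0.87.

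**Protocol definition.** Only the PHQ-9 step matters. Assume 40% are PHQ-2 positive and 35% of those have PHQ-9 of 10 or more, so true positivity is 14%. Completion of 95% → 85% gives 13.3% → 11.9%, OR 0.88.

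**If screened meant cascade finished.** Use the same 40% and 35%, with 71.4% of PHQ-9 positives diagnosed (0.40 x 0.35 x 0.714 = 0.10), and both steps falling from 95% to 85%. Unfinished before: 0.40 x 0.05 + 0.40 x 0.95 x 0.35 x 0.05 = 0.02665. After: 0.40 x 0.15 + 0.40 x 0.85 x 0.35 x 0.15 = 0.07785. Prevalence among finishers is 0.09025/0.97335 = 9.27% and 0.07225/0.92215 = 7.83%, OR 0.83. The bias shrinks but stays, because everyone removed was PHQ-2 positive.

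**Chance of p < 0.05 with no true effect.** This is a linear stepped-wedge approximation with 300 screened per clinic-step, arms of 3/3/3/3/2 clinics, ICC 0.05, CAC 0.80 and a normal test. It indicates the size of the problem and is not the planned permutation test. With period effects the standard error is 0.0133. A one-step fall from 95% to 85% (1 percentage point in prevalence) raises the chance from 5% to about 12%, and 90% to 70% (2 points) to about 32%. The SAP formula for outcome 1 shows no period term; without one the standard error is 0.0084 and the figures are about 22% and 67%.

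**The case against.** The strongest reply is that nothing in the documents says completion will change. No rate is given. The protocol has PHQ-2 positives go on to the PHQ-9 at once, and all counsellors are trained in the model partly to balance the burden. This stands, and it makes the bias conditional. A reader might infer that the weekly PM+ sessions will draw counsellors away from screening, so that the bias favours the intervention. That is conjecture. Completion could as well rise once treatment is on offer, and that would hide benefit.

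The zero-otherwise coding is explicit only in the unadopted joint model, and the term screened is undefined. This also stands, and defining it is the first repair. But nothing elsewhere codes unfinished cascades differently, and the narrower reading does not remove the bias.

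The odds ratio of about 0.79 needs both steps to fall and the SAP's case definition. It should not be read as the expected size; under the protocol's definition the same fall gives about 0.88.

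Three further inferences go too far:
- That the missing-data section covers only missed appointments. It also names data entry error and provides for imputation; the gap is that an unfinished cascade is not among the mechanisms it addresses.
- That the block summaries reveal nothing. Flat completion across blocks would be reassuring. What they cannot do is separate state from time.
- That item 1d ("Proportion screening positive on PHQ-9, out of those who were administered the PHQ-2") is wrong. It is a legitimate descriptive yield, and positivity among those tested is recoverable as 1d / (1b x 1c).

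**Conclusion.** The concern holds as a conditional bias in a primary outcome. Under the SAP's definition, loss at either counsellor step is recorded as absence of depression; under the protocol's definition, loss at the PHQ-9 step is. The plan expects such losses and measures them, but does not carry them into the analysis of outcome 1.

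Neither size nor sign can be fixed from the documents. The range shown, an odds ratio of about 0.76 to 1.14 at 10% true prevalence with no real effect, rests on assumed completion rates. If completion does not differ by clinic state, delta_1 is essentially unaffected. This should be fixed before the analysis. It does not show that the prevalence result will be wrong, and it does not require replacing the primary estimator.

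**What to change.** 1. State what makes a patient count in n_jt and what makes a case, and reconcile the protocol's Primary Outcomes with the SAP's Aggregate cluster-time outcome. Under the protocol's wider denominator, active patients who were never screened would also count as not depressed, so the definition must settle that too.
2. Pre-specify a sensitivity analysis of outcome 1 in which an unfinished cascade is missing, not a non-case. Multiply impute status by stage reached, from cascade counts kept by clinic-step, and fit the planned binomial model to the completed counts. Pool across steps or similar clinics where numbers are small, since some sites serve only 50 to 250 patients a year. Add best-case and worst-case bounds.
3. Report items 1a to 2b by clinic state within each three-month block. Item 1d can stay as it is.

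In the two-step illustration, imputing at the rates seen in completers returns 0.40 x 0.35 x 0.714 = 10% in both states, so OR 1.00. The bounds are much wider. Prevalence before the switch lies between 9.03% and 9.03 + 2.67 = 11.69% (from unrounded values), and after it between 7.23% and 7.23 + 7.79 = 15.01%, so the OR lies between 0.59 and 1.78. The bounds show how much rests on the imputation; they will rarely settle the question.

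**Cost.** SAP wording and modest extra analysis. The addendum already needs cascade counts overall and by block, but the main text speaks of two totals per clinic-step, so the sponsor must confirm that the stage counts are kept at that level. The imputation assumes that incompletes resemble completers at the same stage, and intervals will widen.

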Arm 5	Pre	Pre	Pre	Pre	Pre	Pre	Pre	Pre	Pre	Pre	Pre	Pre	Pre	Pre	Pre	Int	Int	Int	Post	Post	Post	Post	Post	Post	Post	Post	Post	Post	Post	Post

Legend: Pre-intervention (light green), Intervention (red), Post-intervention (light blue), 6-month follow-up (medium blue), 12-month follow-up (dark blue)

Footnote: Each arm represents 2-3 health clinics that have been randomized to that particular arm.

A schedule of trial activities is shown in Table 1. Within each cluster, we will use an open cohort design of individual participants who screen positive for potential depression. All attendees at each clinic will be screened at each time point and screen-positive patients will enter the cohort and be followed for the rest of the study—including after initiation of depression care at their site to assess how depression and depression alleviation relate to our primary (depression symptom alleviation; alleviation of functional impairment) and secondary

(HIV patients: viral load; hypertension patients: systolic blood pressure; diabetes patients: A1C or blood glucose levels; all patients: health utility index) outcomes, as well as processes of care (treatment uptake; adherence; perceived mental health stigma). Furthermore, prior to receipt of depression care, as well as six months later, one household member per participant will be interviewed in order to examine changes in their mental and physical health status. A cost-effectiveness analysis will be used to examine the incremental cost of integrated depression care (IC3D) over and above usual care within the IC3 framework.

Randomization, Allocation and Blinding

Health clinics will be randomly allocated to the five arms, the roll-out of which is spaced apart at 3-month intervals, with one exception: 13 potential combinations will be restricted from this algorithm, due to logistical considerations in the geographical layout of Neno District (note that over a quadrillion theoretical permutations are retained). This randomization will be executed by the project principal investigators using a random sequence generator in Stata 15.²⁹

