Overall health. A health profile will be generated for each individual enrolled in IC3D, using the EQ-5D-5L⁶⁶—previously validated in Malawi.⁶⁷ This survey determines patients' overall health at time of interview and offers a cross-walk to quality-adjusted life years (QALYs).⁶⁸

Secondary Outcomes

Secondary outcomes will constitute those measuring *indirect* benefits and costs of treatment. Indirect benefits will be incorporated into cost-effectiveness estimates by internalizing improvements among comorbid conditions such as HIV and hypertension, as well as reduced household burden of care.

ART adherence. ART adherence will be measured in terms of whether HIV+ enrollees have returned to an IC3 for antiretrovirals (ARVs) within the past three months or else defaulted, an approach considered more reliable than self-reports.^{69,70} This interval overlays

with clinical protocols throughout Malawi in terms of the duration for which ARVs are supplied.

Viral load. Viral load will be measured as part of HIV+ patients' clinical assessment pre-intervention, post-intervention, 6- and 12-month follow-up, consistent with ongoing care at IC3s. This is considered a key metric for determining treatment plans and is highly sensitive to compliance with prescribed ART regimens.⁷¹

HIV disease staging. Staging will be evaluated every three months among HIV+ enrollees, consistent with IC3 visits. This approach to tracking disease progression is commonly used in low-resource settings.⁷²

Chronic care outcomes. Chronic care outcomes on hypertension, type-2 diabetes, and epilepsy will be abstracted from electronic medical records. Systolic blood pressure and adherence to antihypertensive medication (measured by adherence to clinic visits with medication dispensing) will be measured among those with hypertension. Among those with type-2 diabetes, adherence to quarterly visits with medication dispensement and A1C (or random blood sugar) levels will be abstracted. Among those with epilepsy, we will catalog number of reported seizures in past quarter, and adherence to antiepileptics as measured by quarterly medicine pickups.

Household burden of care. Lastly, household burden of care will be evaluated with household members using a locally-adapted version of the Burden Assessment Schedule (BAS),¹⁵ previously implemented by the team.¹⁷ The survey assesses dimensions of emotional and functional burden of care, including missed work, guilt and worry.

Mediators and Moderators

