The data from the trial will be analyzed using a generalized linear mixed model framework, which is standard for stepped-wedge cluster designs.^{87,88} The patients participating form an open cohort with repeated measures, as it will be possible to link each patient taking a PHQ-9 screening and any subsequent exams over time. The models will be at the patient-level, nested within clinic-months and clinics. The primary outcomes are: (i) prevalence of depression; (ii) depression severity (PHQ-9 score) conditional on having depression; (iii) WHODAS score conditional on having depression; and (iv) utility score (0 to 1) from the EQ-5D-5L. The first outcome is a dichotomous event for if the patient has depression or not, while the remaining outcomes are treated as continuous. For the principal analysis of the trial, we used the “complete” stepped-wedge of data from months 1 to 18; long-term follow-up will constitute a secondary analysis.

We specify the following model for patient $i = 1, \dots, N$ in clinic $j = 1, \dots, J$ at time period $t = 1, \dots, T$:

$$y_{ijt} \sim F(g(\eta_{ijt}))$$

$$\eta_{ijt} = \mu + x'_{ijt}\beta + z'_{jt}\gamma + \delta D_{(i)jt} + \theta_i + \alpha_j + \phi_{jt} + \tau_t$$

where y_{ijt} is the outcome, $F(\cdot)$ is an appropriate likelihood and $g(\cdot)$ is a suitable link function, x_{ijt} and z_{jt} are respectively patient and clinic level covariates, τ_t are monthly fixed effects, and $\theta_i \sim N(0, \sigma_\theta^2)$, $\alpha_j \sim N(0, \sigma_\alpha^2)$, and $\phi_{jt} \sim N(0, \sigma_\phi^2)$ patient-, clinic-, and clinic-time random

effects term. We will take both intention to treat (ITT) and per protocol approaches. For the ITT analysis, the variable D_{jt} is an indicator equal to one if cluster j is in the intervention state at time t and zero otherwise, thus δ represents our estimated treatment effect. For per protocol analysis D_{ijt} will be a patient-level variable equal to one if the clinic was in the intervention state and the patient completed the treatment as defined above, and zero otherwise. For dichotomous outcomes, we will use a Bernoulli distribution with logistic link function, for continuous outcomes a normal distribution with identity link function. The same models will be used for secondary outcomes.

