Health measures will be converted to quality-adjusted life years (QALYs) using the EQ-5D-3L cross-walk between domain-specific outcomes.¹¹ QALY estimates will be related to base case and treatment cost estimates. For formal CEA, we will use a gold standard Markov chain Monte Carlo (MCMC) simulation-based approach⁹⁴ in TreeAge,⁹⁵ from a societal perspective.⁹⁶ For sensitivity analyses, we will vary discount rates from 0-5%, based on health-adjusted life expectancy.⁹⁷ Unit of interest is the incremental cost-effectiveness ratio (ICER) of cost per QALY, comparing the cost of integrated chronic care before and after introduction of the depression treatment.

Ethics

The study protocol has been reviewed and approved by the National Health and Science Research Council administered by the Government of Malawi, and by the RAND Corporation in Santa Monica, California. Any protocol modifications will be submitted to the IRB for review,

and participants will be informed if warranted. The trial is registered with the NIH clinical trial registry (clinicaltrials.gov) and assigned the number NCT04777006.

We do not expect any medication-related adverse events beyond that of routine medical care and use of antidepressant therapy. All potential side effects will be outlined to patients during the informed consent process. Patients will be assessed and monitored with regards to psychiatric symptoms and treatment side effects by their provider on a standardized schedule using the Antidepressant Side Effect Checklist.

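### The SAP limits the EQ-5D utility outcome to patients who screen positive at that visit, while the Protocol defines it without that condition

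*SAP*

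**What the plan says.** **Protocol.** Under Primary Outcomes (Overall health): "A health profile will be generated for each individual enrolled in IC3D, using the EQ-5D-5L". The same section says survey measures are given at each assessment unless noted otherwise. Analysis of Intervention Effects lists four primary outcomes. PHQ-9 severity is conditional on depression, and so is the third outcome, "WHODAS score conditional on having depression". The fourth carries no such condition: "iv) utility score (0 to 1) from the EQ-5D-5L". Study Design says that people who screen positive enter the cohort and are followed to the end of the study, including after depression care starts at their site.

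**SAP.** Analysis of Primary Outcomes lists four outcomes, the last being "EQ-5D-3L utility score and those with depression". The section on individual-level outcomes then says that outcomes 2 to 4 are taken only from patients who screen positive at the scheduled visit. The Appendix repeats this and adds that the instruments are not used for anyone else in the trial.

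**Instrument.** The Protocol names the 5L version wherever it describes collection. Its cost-effectiveness section obtains QALYs "using the EQ-5D-3L cross-walk between domain-specific outcomes". The SAP names the 3L version. Neither document names a value set.

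**Status.** The Protocol's Introduction names only depression symptoms and functional impairment as primary, and Study Design puts "all patients: health utility index" among the secondary outcomes. Every other place that assigns a status to the EQ-5D, in both documents, makes it primary.

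**The concern.** Whether a patient screens positive at a given visit is determined after randomisation, and lowering that probability is the purpose of the intervention. The SAP itself expects prevalence to fall. If utility is recorded only at positive visits, the intervention and control means come from differently selected patients. Those whose utility has probably improved most are absent, and more of them are absent under the intervention. Randomisation of clinics does not protect such a comparison.

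This cannot be repaired at the analysis stage. If the questionnaire is not given to a recovered cohort member, the Protocol's outcome (iv) does not exist for that patient-visit, nor does a directly measured utility for the QALY calculation. The difference therefore has to be settled in data collection as well as in wording.

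**Working it through.** **1. The plan's own figures.** The only visible size figure is 420 enrollees per step, and 14 clinics × 30 = 420 agrees. It has no bearing on this point. The minimum detectable effects in Protocol Table 2 are not in the text available, and no EQ-5D effect or standard deviation is given. The discrepancy is therefore established by comparing text, and its size can only be illustrated.

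**2. Population, side by side.**

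- Protocol, Overall health: every enrolled individual.
- Protocol, Analysis of Intervention Effects: conditioning on (ii) and (iii), none on (iv). As the four stand in one sentence, the omission reads as deliberate.
- SAP, Analysis of Primary Outcomes: those with depression. Alone, this could mean anyone ever diagnosed, which would come close to the Protocol.
- SAP, individual-level outcomes, and Appendix: positive at that visit. These two places rule out the generous reading.

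**3. Instrument, side by side.** 5L is collected in the Protocol and 3L analysed in the SAP. The Protocol's 3L cross-walk for QALYs would reconcile them if the SAP means 5L responses scored through it, but neither document says so.

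**4. Illustration of size.** Assumptions, none from the documents:

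- severity S among enrolled patients at follow-up is N(0, 1) in the control state and N(−d, 1) under the intervention, with d = 0.3 to 0.5;
- utility is −ρS plus noise, with ρ = 0.4 to 0.6, so treatment affects utility only through severity;
- utility is recorded only if S > c, with c set so that a proportion p = 0.3 to 0.7 of control-state enrollees are still positive.

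Effect in all enrolled: ρd.

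Effect among those positive: ρ[m(0) − m(−d)], where m(μ) = μ + φ(c − μ)/[1 − Φ(c − μ)].

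Example with p = 0.5 (c = 0), d = 0.3, ρ = 0.4:

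- m(0) = 0.3989/0.5 = 0.798
- m(−0.3) = −0.3 + 0.3814/0.3821 = 0.698
- positive-only effect = 0.4 × (0.798 − 0.698) = 0.040
- all-enrolled effect = 0.4 × 0.3 = 0.120
- ratio = 0.33

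In this example 50% of control-state and 38% of intervention-state enrollees supply a value. Over the range, with the lower ratio for d = 0.5 and the higher for d = 0.3:

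| p still positive (control) | Ratio, positive-only to all enrolled |
|---|---|
| 0.7 | 0.43 to 0.45 |
| 0.5 | 0.31 to 0.33 |
| 0.3 | 0.23 to 0.24 |

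ρ cancels from the ratio. A direct effect of treatment on utility, not through severity, would bring the ratio nearer to 1. If treatment cleared mainly the milder cases, those left would be sicker and the ratio could fall further. The illustration compares two cross-sections and does not model the patient random effects.

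**The case against.** Four arguments on the other side have weight.

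- **The restriction is not peculiar to the EQ-5D.** Both documents condition PHQ-9 severity and WHODAS on depression, so recovered patients are lost there too, and prevalence is there to capture recovery. This stands as far as it goes. But prevalence does not measure recovery in utility units, and only for outcome 4 do the two documents define different populations.
- **All enrolled is not itself a settled population.** Study Design's phrase "all patients: health utility index" sits beside HIV, hypertension and diabetes patients, so it probably means regardless of comorbidity and says nothing about current depression. The point does not rest on it. Protocol, Treatment: IC3D also says that enrolled people who no longer meet criteria when treatment starts leave the cohort. That stands, and the fix must deal with it.
- **3L may be only a scoring label.** A reader might infer that the questionnaire was changed. The documents do not support that. What remains is an unstated scoring rule for a primary outcome.
- **The multiplicity family is fixed.** From the summary text, a reader might infer that it is open whether utility belongs in the stepdown family. It is not: the Protocol's analysis section and the SAP list the same four primary outcomes and apply the stepdown to them. The contrary wording is confined to the Protocol's Introduction and Study Design. Bonferroni thresholds for smaller families are beside the point, since the plan reports permutation-based adjusted p-values.

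A reader might also infer that the QALYs will come from a different population than the trial's utility effect. The cost-effectiveness section does not say which patients supply them, so this cannot be concluded.

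**Conclusion.** The concern holds for the population of outcome 4. The Protocol's utility outcome is unconditional on depression, whereas the SAP's exists only for patients positive at that visit. The SAP version compares groups selected by a consequence of treatment and would probably understate the utility effect in the enrolled cohort. The ratio of 0.23 to 0.45 shows that the loss could be large, but it depends wholly on the stated assumptions and is not an estimate for this trial.

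The instrument mismatch is real but minor, and one sentence could resolve it. The conflict over status lies inside the Protocol's summary text and leaves the four-outcome family intact. The change should be made, because this is one of four primary outcomes and the missing values cannot be recovered later.

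**What to change.** **In the SAP.**

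- Define outcome 4 as the EQ-5D-5L utility, scored with one named value set or cross-walk that is also used for the QALYs.
- Analyse it in all cohort members at every quarterly assessment, whatever their PHQ-9 that day.
- State how people who leave the cohort at treatment initiation are handled. If their later utilities are dropped, selection on recovery returns at the point where a clinic switches.
- Amend the recording rule under individual-level outcomes and in the Appendix so that the EQ-5D is given at visits where a cohort member does not screen positive.
- Keep the screen-positive analysis as supplementary. It also covers early visits at which the EQ-5D was not collected.

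**In the Protocol.** Correct the Introduction and Study Design to match the four primary outcomes in the analysis section.

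**Cost.** This is more than wording, because it adds a short questionnaire at visits that are already scheduled. Recruitment was anticipated from 15 July 2021 and the Protocol is dated 20 September 2021, so some early visits may lack the EQ-5D for patients who were not positive. Such gaps would fall mainly in control-state data and should be counted by period and treatment state. Outcome 4 will also cover a wider population than outcomes 2 and 3, which the report should say.
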